#### 3.1.1.2. Population of Subjects Targeted by the Clinical Question

The population targeted by the clinical question is defined through Randomized subjects with CHrEF (EF≤40%) who received at least one dose of CRD-740 or placebo (mITT).

# 3.1.1.3. Variable Obtained from Each Subject Required to Address the Clinical Question

For each subject in the study, the variable to address the clinical question is change from baseline in plasma cGMP AUC at Week 4.

CONFIDENTIAL

# 3.1.1.4. Handling of Intercurrent Events to Reflect the Clinical Question of Interest

Intercurrent events will be handled through a treatment policy and while on treatment strategy. The following intercurrent events are anticipated during the study:

- Discontinuation of treatment
- Subject withdraws consent from further data collection
- Subject lost to follow-up

The following table describes how intercurrent events will be collected and handled within the analysis.

Table 2 Handling of Intercurrent Events for the Primary Efficacy Estimand

Intercurrent event	Data collection and analysis
Discontinuation of treatment	Patients will be followed, and data collected after the intercurrent event will be used in analysis in line with a treatment policy strategy, i.e., disregarding the occurrence of the intercurrent event
Subject withdraws consent from further data collection	Subject who withdraws consent from further data collection will be analyzed by while on treatment strategy: only plasma cGMP values collected before the occurrence of the intercurrent event will be included in the analysis.
Subject lost to follow-up	Subject who is lost to follow-up will be analyzed by while on treatment strategy: only plasma cGMP values collected before the occurrence of the intercurrent event will be included in the analysis.

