2.3. Estimands

The ICH ⁹ E9 (R1) addendum on estimands ¹⁰ and sensitivity analysis in clinical studies analysis in clinical studies to the guideline on statistical principles for clinical studies became effective on 30 July 2020. Table 1 address the construction of estimands for the primary objectives for Part A

FINAL 10 AUG 2022 Page 29 of 73

[figure not shown]
Protocol CONFIDENTIAL Labcorp Study: 8459270 Sponsor Reference: CRD-740-201

Table 1: Estimands for primary objectives for Part A

Objectives	Estimands/Endpoints
Primary	
To assess the effect of CRD-740 compared to placebo in plasma cGMP at Week 4 in subjects with CHFrEF.	Endpoint: The change from baseline (Day -1) in plasma cGMP at Week 4
	Population : Randomized subjects with CHrEF (EF≤40%) who received at least one dose of CRD-740 or placebo (mITT)
	Treatment: CRD-740 dose or placebo, with or without sacubitril/valsartan, dosed as required.
	Intercurrent Event Strategy:
	Discontinuation of treatment (Treatment policy strategy)
	Subject withdraws consent from further data collection (While on treatment strategy)
	Subject lost to follow-up (While on treatment strategy)
	Population Level Summary : Treatment difference (CRD-740 – placebo) in change from baseline in plasma cGMP values at Week 4.
To assess the safety and tolerability of CRD-740 in subjects with CHFrEF, defined as heart failure with EF ≤40%.	Endpoint: AEs, physical examinations, vital signs, 12-lead electrocardiograms, laboratory safety tests (biochemistry, urinalysis, and hematology)
	Population : Subjects with CHFrEF (EF≤40%) who received at least one dose of CRD-740 or placebo
	Treatment: CRD-740 dose or placebo, with or without sacubitril/valsartan, dosed as required.
	Intercurrent Event Strategy:
	Discontinuation of treatment (Treatment policy strategy)
	Subject withdraws consent from further data collection (While on treatment strategy)
	Subject lost to follow-up (While on treatment strategy)
	Population Level Summary : The proportion of subjects who experience any AE, the proportion of subjects who experience any SAE and the exposure-adjusted incidence rates for AE and SAE in each treatment and dose level group.

[figure not shown]
Abbreviations: AE = adverse event; cGMP = cyclic guanosine monophosphate; CHFrEF = chronic heart failure with reduced ejection fraction; EF = ejection fraction; mITT = modified Intention to Treat; SAE = serious adverse event

FINAL 10 AUG 2022 Page 30 of 73

[figure not shown]

CONFIDENTIAL

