#### 5.2. Handling of Dropouts, Missing Data, and Outliers

#### 5.2.1. Handling of Missing Efficacy Data

For Part A, missing efficacy data will not be replaced for the primary efficacy analysis.

For sensitivity analysis of the efficacy endpoints in Part A (efficacy endpoints of NT-proBNP, BNP, and urine and plasma cGMP), inference will be done using mixed-effects models repeated-measures, which assumes that missing outcomes are missing at random (MAR).

\* Except for plasma cGMP and 6-hour urine collection cGMP where baseline is assessed on Day -1. See Section 5.1.2 for details on the baseline definition.

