#### 6.6.1. Primary Efficacy Analysis

#### Part A:

The primary endpoint is the change from baseline in plasma cGMP AUC at Week 4. Blood samples for cGMP are collected at Visit 2, Visit 3, Visit 5 and Visit 7 on specific timepoints (pre-dose, 1 hr, 2 hr, 3 hr, 6 hr post dose). AUC0-6 will be derived from those timepoints at each visit using the linear trapezoidal rule.

The change in plasma cGMP AUC0-6 will be compared between CRD-740 and placebo in the mITT population using an analysis of covariance (ANCOVA) model with fixed factors for treatment (2 levels), and Entresto use at baseline (2 levels), and covariates for baseline EF, and baseline plasma cGMP AUC.

The analysis will be repeated on the change from baseline in plasma cGMP AUC at Week 2.

CRD-740 will be analyzed as one treatment group even though CRD-740 consists of two weeks of treatment with CRD-40, followed by two weeks of treatment with CRD-740.

CONFIDENTIAL

The least square means of the change from baseline for each treatment group, along with the 95% confidence intervals (CI), and the least square mean treatment difference and the associated 95% CI for this difference will come from the ANCOVA model.

Observed values and absolute change from baseline at each analysis visit for plasma cGMP AUC will be summarized by treatment group using default summary statistics for continuous variables on the mITT population.

Absolute change from baseline at each analysis visit for plasma cGMP AUC will be plotted by treatment group using mean and standard error for continuous variables on the mITT population.

cGMP data will be listed for mITT population.

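### Withdrawal and loss to follow-up are labelled while-on-treatment, but the primary ANCOVA is fixed at Week 4 and leaves out anyone without a Week 4 AUC

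*SAP*

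**What the plan says.** - **Strategy.** SAP 3.1.1.4 (Table 2) has a subject who withdraws consent or is lost to follow-up analysed by a while-on-treatment strategy, so that "only plasma cGMP values collected before the occurrence of the intercurrent event will be included in the analysis". Protocol 2.3 (Table 1) lists the same strategy for withdrawal of consent and for loss to follow-up. Stopping treatment is a separate event, handled by treatment policy.
- **Variable and population.** SAP 3.1.1.3 states that "the variable to address the clinical question is change from baseline in plasma cGMP AUC at Week 4". SAP 3.1.1.5 fixes the treatment difference at the same time point. The target population (3.1.1.2) is every randomized and dosed subject.
- **Primary analysis.** SAP 6.6.1: "The primary endpoint is the change from baseline in plasma cGMP AUC at Week 4". That change "will be compared between CRD-740 and placebo in the mITT population using an analysis of covariance (ANCOVA) model", with terms for treatment, Entresto use, baseline EF and baseline cGMP AUC.
- **Missing data.** SAP 5.2.1: for Part A, "missing efficacy data will not be replaced for the primary efficacy analysis".
- **Sensitivity analysis.** SAP 6.6.2 plans an MMRM over Visits 3, 5 and 7 in mITT, on log and raw scales, with treatment differences at all visits. Its listed terms include baseline EF but not baseline cGMP AUC. SAP 5.2.1 gives its assumption as missing at random. The readable text of SAP 3.1.1.6, on sensitivity estimators for this estimand, names only the per-protocol repeat.

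**The concern.** A while-on-treatment strategy redefines the variable as the response up to the event. Here the variable stays at Week 4, and the model takes one Week 4 change per subject. For early leavers the label therefore has nothing to act on: they belong to the target population but supply no outcome.

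Two things are at stake. First, the clinical study report would state an estimand that the primary analysis does not estimate, and the analysis that is run states no missing-data assumption. Second, if early loss depends on response and differs between arms, the contrast among subjects with a Week 4 AUC is biased. The one planned model that could use their earlier profiles lacks the ANCOVA's baseline cGMP covariate and is not tied to this estimand.

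**Working it through.** **Step 1. Trace one subject lost at Day 20.**

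| Question | Source | Answer |
|---|---|---|
| In the target population? | SAP 3.1.1.2 | Yes, dosed |
| AUC0-6 available? | Protocol Appendix 4, SAP 6.6.1 | Day -1, Day 1, Day 15 |
| Can Day 15 count as Week 4? | SAP Table 4 | No; the window is Day 25 to Day 43 |
| Does the exit visit give an AUC0-6? | Protocol 4.3.4 and Appendix 4 | No; Visit 9 procedures show one cGMP entry and no 0-6 h time points |
| Is the gap filled? | SAP 5.2.1 | No |
| In the primary ANCOVA? | SAP 6.6.1 | No |
| Earlier AUCs used anywhere? | SAP 6.6.1, 6.6.2 | Week 2 ANCOVA, summaries, sensitivity MMRM |

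SAP section 7 (changes to the planned analysis) does not mention the point.

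**Step 2. What the label would mean if carried out.** Assume a true effect of 0.5 at Week 2 and 1.0 at Week 4, with leavers contributing their Week 2 change and loss unrelated to response. The estimated effect is 1.0 - (active loss) x (1.0 - 0.5):

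- 10% active loss: 1.0 - 0.10 x 0.5 = 0.95
- 20% active loss: 1.0 - 0.20 x 0.5 = 0.90

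Simulation gave 0.95 (10% active, 5% placebo) and 0.90 (20%, 10%), against 1.00 for the Week 4 ANCOVA. These are different quantities. The literal version also mixes points on either side of the Day 15 dose escalation.

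**Step 3. Precision.** The plan states no power, effect size, SD or dropout rate, so there is no plan figure to reproduce. Sixty subjects at 2:1 give 40 and 20. In SD units, SE = sqrt(1/n1 + 1/n0); for 40 and 20 this is sqrt(0.025 + 0.05) = 0.274.

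| Assumed loss, both arms | Left (active/placebo) | SE | Increase |
|---|---|---|---|
| 5% | 38/19 | 0.281 | 2.6% |
| 10% | 36/18 | 0.289 | 5.4% |
| 15% | 34/17 | 0.297 | 8.5% |
| 20% | 32/16 | 0.306 | 11.8% |

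The loss of precision is modest.

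**Step 4. Bias when loss depends on response in the active arm only.** Let Z be the standardised Week 2 response and ρ its correlation with the Week 4 response. Let the chance of leaving be π(Z) = 1/(1 + exp(Z - a)), so the odds rise 2.7-fold per SD of lower response, and let p be the mean of π. For normal Z, the mean of Z among stayers is E[π(1 - π)]/(1 - p), and the bias is ρ times that. Placebo loss (5%) is taken as unrelated to response and adds nothing.

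- p = 0.10 (a = -2.56): 0.0817/0.90 = 0.091; times 0.5 and 0.7 gives 0.045 and 0.064 SD.
- p = 0.20 (a = -1.65): 0.1386/0.80 = 0.173; times 0.5 and 0.7 gives 0.087 and 0.121 SD.

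Simulations of 40 v 20 subjects under similar assumptions gave 0.04 to 0.08 SD and 0.09 to 0.15 SD. If high responders leave instead, the formula gives the same sizes with a minus sign; simulation at 10% v 5% gave -0.05 to -0.07 SD. With loss unrelated to response, or the same rate and selection in both arms, the bias was about 0. A likelihood estimator that also uses Week 2 had bias of about 0 in the low-responder settings, with an equal or slightly smaller SE (about 0.28 SD).

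**Step 5. Can the MMRM serve as written?** Three visits give an unstructured covariance 3 x 4/2 = 6 parameters, which already describes any pattern. SAP 6.6.2 also lists random intercept and slope, which would add up to 3 more (two variances and a covariance) that the data cannot separate from the first 6.

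**The case against.** - **The word only.** Table 2 can be read as barring data after the event, not as promising that earlier AUCs enter the Week 4 model. That reading avoids a literal contradiction. It leaves the while-on-treatment label empty, however, because these subjects supply no outcome.
- **Earlier data are used.** A reader might infer that the Day 1 and Day 15 profiles are discarded. They are not: they enter the Week 2 ANCOVA and both MMRMs, which give contrasts at every visit including Week 4. This stands. The gap is confined to the primary ANCOVA and its repeats in other populations, and to the MMRM's missing covariate and undefined role.
- **Poor tolerability does not by itself remove a subject.** Protocol 4.3.3 asks those who stop drug to continue visits, and Table 2 keeps their data. This stands; only consent withdrawal or loss before a Week 4 AUC matters.
- **Direction.** A reader might infer that the primary result favours the drug. The documents do not support that: they give no dropout rate or pattern, and the sign reverses if high responders leave.
- **Consequence.** Part A was not sized by power (SAP 2.3) and Part B will not be conducted (SAP 2.1). This limits the stakes but does not remove the mismatch in a primary estimand.

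**Conclusion.** The mismatch is real. The strategy stated for withdrawal and loss to follow-up is not carried out by the primary analysis, which is in effect an analysis of subjects with both Day -1 and Week 4 AUCs under an unstated missingness assumption. It affects only those who leave before a Week 4 AUC exists.

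Under assumed losses of 10% to 20% active against 5% placebo, the bias is roughly 0.05 to 0.15 SD in either direction if loss depends on response in one arm, and about 0 otherwise. Against an SE near 0.28 SD, that is about 0.2 to 0.5 of a standard error (0.05/0.28 and 0.15/0.28). These sizes rest entirely on assumed dropout and correlation. With no early loss the two estimators target and estimate the same thing.

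Relabelling alone changes no result. The useful gain is a Week 4 estimate that uses the earlier profiles and is matched to the ANCOVA. This should be corrected, but it does not invalidate the primary analysis.

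**What to change.** 1. In SAP Table 2 and protocol Table 1, treat withdrawal of consent and loss to follow-up as missing data rather than as events with a while-on-treatment strategy. In SAP 5.2.1 and 6.6.1, state that the ANCOVA uses subjects with Day -1 and Week 4 AUC. State also that it assumes Week 4 values are missing independently of their outcome given treatment, Entresto use, baseline EF and baseline AUC.
2. In SAP 6.6.2, add baseline cGMP AUC and its interaction with visit to the raw-scale MMRM over Visits 3, 5 and 7. Use one covariance specification: unstructured, without the added random intercept and slope.
3. In SAP 3.1.1.6, name that model's Week 4 contrast as the missing-at-random estimator of the primary estimand, and report it beside the ANCOVA.

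**Cost.** Wording in two tables and a few SAP sections, one covariate with its interaction, and one more model assumption to state. The covariate is already collected and used in the ANCOVA. The SAP plans the MMRM, but nothing in the documents shows that it has been programmed, so some programming should be allowed for.

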# 3.1.1.5. Population-level Summary for Comparison between Treatment Conditions

The treatment effect will be quantified by the Treatment difference (CRD-740 – placebo) in change from baseline in plasma cGMP AUC values at Week 4.

#### 3.1.1.6. Sensitivity Estimators for the Primary Efficacy Estimand

[figure not shown]
A sensitivity analysis of the primary endpoint will be performed on the Per Protocol Population analysis.

CONFIDENTIAL

### 3.1.2. Estimands for the primary safety objective

The estimand for the primary safety objective (assessment of the safety and tolerability of CRD-740 in subjects with CHFrEF, defined as heart failure with EF  $\leq$ 40%) is defined through the 5 attributes described in Sections 3.1.2.1 to 3.1.2.5:

#### 3.1.2.1. Treatment Condition of Interest

#### 3.1.2.2. Population of Subjects Targeted by the Clinical Question

The population targeted by the clinical question is defined through Subjects with CHFrEF (EF≤40%) who received at least one dose of CRD-740 or placebo.

# 3.1.2.3. Variable Obtained from Each Subject Required to Address the Clinical Ouestion

For each subject in the study, the variables to address the clinical question are AEs, physical examinations, vital signs, 12-lead electrocardiograms and laboratory safety tests (biochemistry, urinalysis, and hematology).

# 3.1.2.4. Handling of Intercurrent Events to Reflect the Clinical Question of Interest

Intercurrent events will be handled through a treatment policy and while on treatment strategy. The following intercurrent events are anticipated during the study:

- Discontinuation of treatment
- Subject withdraws consent from further data collection
- Subject lost to follow

The following table describes how intercurrent events will be collected and handled within the analysis.

Table 3 Handling of Intercurrent Events for the Primary Safety Estimand

Intercurrent event	Data collection and analysis	
Discontinuation of treatment	Patients will be followed, and data collected after the intercurrent event will be used in analysis in line with a treatment policy strategy, i.e., disregarding the occurrence of the intercurrent event	

CONFIDENTIAL

Intercurrent event	Data collection and analysis	
Subject withdraws consent from further data collection	Subject who withdraws consent from further data collection will be analyzed by while on treatment strategy: only safety data collected before the occurrence of the intercurrent event will be included in the analysis.	
Subject lost to follow-up	Subject who is lost to follow-up will be analyzed by while on treatment strategy: only safety data collected before the occurrence of the intercurrent event will be included in the analysis.	

# 3.1.2.5. Population-level Summary for Comparison between Treatment Conditions

The treatment effect will be quantified by the proportion of subjects who experience any AE, the proportion of subjects who experience any SAE and the exposure-adjusted incidence rates for AE and SAE in each treatment and dose level group.

### 3.1.2.6. Sensitivity Estimators for the Primary Safety Estimand

No sensitivity analyses will be conducted for primary safety estimand in part A.

CONFIDENTIAL

## 4. Analysis Populations

In accordance with ICH E3 and E9, the following analysis populations will be used for the analyses.

## 4.1. All Screened Population

The All Screened Population will include every subject who has signed the informed consent form. The All Screened Population will be used for summaries of disposition and the associated listing.

### 4.2. Intention to Treat Population

The Intention to Treat Population (ITT) population will consist of all randomized subjects. Subjects will be analyzed according to their randomized treatment, regardless of actual treatment received, treatment compliance, or treatment duration. The ITT population will be used for summaries of disposition, protocol deviations, demographics & baseline characteristics, medical history, and prior/concomitant medications.

## 4.3. Modified ITT Population

The modified Intention to Treat (mITT) Population will consist of all randomized subjects who received at least one dose of CRD-740 or placebo. Subjects will be analyzed according to their randomized treatment, regardless of actual treatment received, treatment compliance, or treatment duration. The mITT population will be used as the primary efficacy population.

#### 4.4. Per Protocol Population

The Per Protocol Population (PP) will consist of all mITT subjects with no important protocol deviations. Subjects will be analyzed according to their randomized treatment. The PP Population will be used for sensitivity analyses.

Protocol deviations are defined as any change, divergence, or departure from the study design or procedures defined in the study protocol. Important protocol deviations are a subset of protocol deviations which may significantly impact the correctness, accuracy, and / or reliability of the study data or that may significantly affect a subject's rights, safety, or well-being. Section 4.4.1 details the deviations.

#### 4.4.1. Important Protocol Deviations Leading to Exclusion from the PP Population

Deviations from the protocol, as defined in the protocol and / or protocol deviation plan, will be documented by the trial monitors and project management throughout the trial period.

CONFIDENTIAL

Only those important protocol deviations considered to have a major effect on efficacy will lead to complete exclusion of the patient from the PP Population. For the purposes of this trial, the criteria identified as candidates for important protocol deviations leading to exclusion from the PP Population will be detailed in a separate protocol deviations spreadsheet, as it is considered that the occurrences of any of these criteria might have an important influence on the primary efficacy endpoint. Patients will be assessed purely by comparison of their eCRF data with the defined criteria; protocol waivers will not be taken into consideration (e.g., if a patient younger than 18 enters the trial on a protocol waiver, the patient would still be excluded from the PP Population).

Criteria which require clinical or medical monitoring interpretation will be reviewed prior to database lock. All important protocol deviations leading to exclusion from the PP Population occurring during the trial will be reviewed and approved by Cardurion prior to database lock.

#### 4.5. Week 2 Analysis Population

The Week 2 Analysis Population will consist of all mITT subjects with no important protocol deviations during the first 2 weeks. Subjects will be analyzed according to their randomized treatment. The Week 2 Analysis Population will be used for sensitivity analyses for the interim DMC.

Important protocol deviations are defined as any change, divergence, or departure from the study design or procedures defined in the study protocol that may significantly confound the ability to detect target engagement via pharmacodynamic measures.

#### 4.6. Week 4 Analysis Population

The Week 4 Analysis Population will consist of all mITT subjects with no important protocol deviations during the first 4 weeks. Subjects will be analyzed according to their randomized treatment. The Week 4 Analysis Population will be used for sensitivity analyses for the interim DMC.

Important protocol deviations are defined as any change, divergence, or departure from the study design or procedures defined in the study protocol that may significantly confound the ability to detect target engagement via pharmacodynamic measures.

#### 4.7. Safety Analysis Population (SAF)

The Safety population will consist of all subjects who received at least one dose of CRD-740 or placebo. Subjects will be analyzed according to the treatment first received. The Safety population will be used as the primary safety population.

CONFIDENTIAL

## 4.8. Pharmacokinetics Analysis Population (PK)

The PK population will consist of all subjects who received at least one dose of CRD-740 and have no protocol deviations that are considered to impact the PK results. PK Analysis Population subjects are analyzed according to their randomized treatment.

CONFIDENTIAL

